### **Inclusion Criteria**

1. 18-75 years
2. Confirmed advanced cirrhosis of any aetiology with a MELD score between 12 and 21.  
The diagnosis of liver cirrhosis will be based on clinical, radiological, or histological criteria
3. Patients must be deemed to have capacity to consent to study.

### **Exclusion Criteria**

1. Ongoing bacterial infection requiring antibiotic treatment.
2. Current or history of significant alcohol consumption for a period of more than 2 consecutive months within 6 months prior to screening (significant alcohol consumption is defined as more than 20 g/day in females and more than 30 g/day in males, on average).
3. Treatment with antibiotics or probiotics in the preceding 14 days
4. History of recent spontaneous bacterial peritonitis , gastrointestinal bleeding or overt hepatic encephalopathy (14 days)
5. Previous Liver Transplantation
6. Hepatocellular Carcinoma
7. Human Immunodeficiency Virus (HIV) infection
8. Active or serious medical disease with likely life expectancy less than 5 years
9. Active substance abuse including inhaled or injection drugs in the year prior to screening.
10. Pregnancy, planned pregnancy, potential for pregnancy and unwillingness to use effective birth control during the trial, breast feeding

11. History of severe (anaphylactic) food allergy
12. History of gastroparesis or altered gastric motility
13. Psychiatric disorder
14. Inflammatory bowel disease (IBD)
15. Coeliac disease
16. Immunosuppression e.g. more than two weeks treatment with corticosteroids within 8 weeks of active treatment with tacrolimus, mycophenylate, azathioprine
17. Any other condition which, in the opinion of the investigator, would impede compliance or hinder completion of the study

### **Randomization of patients**

Patients with decompensated cirrhosis who will be enrolled in the study after satisfying the selection criteria will be randomized into two groups 1:1 ratio using a random number generator

**Group 1(Experimental Arm):** Patients with decompensated cirrhosis who will receive Fecal MicrobiotaTransplantation via nasojejunal tube as well as traditional treatment for decompensated cirrhosis.

**Group 1(Standard of Care Arm):** Patients with decompensated cirrhosis who will receive standard medical treatment for decompensated cirrhosis.

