## **Study Protocol:**

**Title:** Single Session of Fecal Microbiota Transplantation in Decompensated Cirrhosis: An open-label randomized control trial

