### **3. AIMS AND OBJECTIVES**

#### **Research question**

Does FMT improve liver functions, prevent complications, reduce levels of pro-inflammatory cytokines and lead to an improvement in prognostic scores (CTP, MELD, MELD Na) and short-term survival in patients with DC?

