**Objectives:**

**Primary Objective:** To assess the difference in 180-day mortality between the FMT group and the SOC group.

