#### **4. METHODOLOGY**

**Study design:** This will be an institute based prospective pilot study carried out in Postgraduate Institute of Medical Education and Research, Chandigarh from July 2018 to June 2020.

**Study period:** 15 months (from August 2018 to November 2019)

**Recruitment Period:** 10 months (August 2018 to May 2019)

**Sample Size:** 20 consecutive patients satisfying the selection criteria in each arm

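### The randomisation method is not fully specified, and baseline MELD is controlled neither in the allocation nor in the analysis of this 40-patient open-label trial

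*Combined protocol and SAP*

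**What the plan says.** The section on randomisation of patients says that patients will be "randomized into two groups 1:1 ratio using a random number generator". In the text available, that is the whole description. It does not say whether the sequence is simple, blocked or a fixed list, whether it is stratified, who prepares and holds it, or when an allocation is revealed.

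The Methodology section sets the sample size at "20 consecutive patients satisfying the selection criteria in each arm" and calls the work an "institute based prospective pilot study". The title describes it as "An open-label randomized control trial".

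The inclusion criteria admit patients "with a MELD score between 12 and 21", so the score is known for everyone before randomisation. The research question lists MELD among the prognostic scores, and the secondary objectives make it an outcome at 28, 90 and 180 days. The primary objective is "To assess the difference in 180-day mortality between the FMT group and the SOC group".

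The Statistical Analysis section plans t or Mann-Whitney tests, chi-square or Fisher tests, and Kaplan-Meier curves with a log-rank test. None of these is adjusted for or stratified by a baseline variable.

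**The concern.** Three things are at stake.

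- **MELD balance.** The protocol itself treats MELD as prognostic. With about 20 patients per arm, chance alone can leave the arms visibly different at entry. Neither the allocation nor the analysis does anything about it, so the mortality, CTP and MELD comparisons would be hard to interpret.
- **Foreseeable allocation.** Treatment is open and there is one centre, so staff can count how many patients each arm has received. If the arms are made to reach 20 by closing whichever fills first, the remaining allocations are known before the patient is enrolled. Exclusion criterion 17 rests on the investigator's opinion, which gives a recruiter who foresees the next arm a discretionary way to act on it.
- **Arm sizes.** If each patient is allocated independently, 20 in each arm is an unlikely result. The stated arm sizes would then not follow from the stated method.

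**Working it through.** **Inputs from the protocol.** 40 patients, 1:1, 20 per arm (Methodology; Randomization of patients); MELD 12 to 21 (Inclusion Criteria). The 20 per arm comes with no effect size, control rate or power, so there is no calculation to reproduce.

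**Assumption.** No MELD distribution is given. Three integer distributions on 12-21 were used: triangular (SD 2.22), right-skewed (SD 2.45) and uniform (SD 2.87).

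**1. Arm sizes, if randomisation is simple.** The number in one arm is Binomial(40, 0.5).

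- P(exactly 20:20) = C(40,20)/2^40 = 12.5%.
- P(18:22 or more uneven) = 63.6%; P(16:24 or more uneven) = 26.8%.
- Information kept relative to 20:20 is 4 × n1 × n0 / 40². For 24:16 it is 4 × 24 × 16 / 1600 = 96%. For 25:15 it is 4 × 25 × 15 / 1600 = 93.75%.

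Exact equality is therefore unlikely, but losing it costs little.

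**2. Foreseeable allocations.** If randomisation is simple and each arm closes at 20, the expected number of forced final allocations is 40 × C(40,20)/2^40 = 40 × 0.1254 = 5.0. With a pre-made random list of 20 and 20, it is 1 + 19/21 = 1.9.

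**3. MELD balance without stratification.** With 20 per arm, the standard error of the difference in mean MELD is SD × √(2/20).

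- SD 2.22: 2.22 × 0.316 = 0.702; P(|difference| ≥ 1) = P(|Z| ≥ 1.42) ≈ 15%.
- SD 2.87: 2.87 × 0.316 = 0.908; P(|difference| ≥ 1) = P(|Z| ≥ 1.10) ≈ 27%.

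Simulation gives slightly higher figures, because MELD takes whole values and a difference of exactly 1 counts.

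**4. Simulation.** 20,000 trials of 40 patients per scheme. The two strata were cut at 17, or at 15 for the skewed case. Entries are P(mean MELD differs by ≥ 1 point).

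| MELD shape (SD) | Simple | Fixed 20/20 list | Stratified, blocks of 4 | Stratified, blocks 2/4 | Stratified, blocks 4/6 |
|---|---|---|---|---|---|
| Triangular (2.22) | 16.3% | 16.4% | 1.7% | 1.5% | 1.7% |
| Right-skewed (2.45) | 20.6% | 20.7% | 2.7% | 2.9% | 3.0% |
| Uniform (2.87) | 28.1% | 28.4% | 3.8% | 3.6% | 4.1% |

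A fixed 20/20 list repairs arm size but leaves mean MELD as exposed as simple randomisation does. A difference of 2 points or more is uncommon without stratification (about 0.5-3%) and close to zero with it.

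The number of patients in the upper MELD stratum differs between arms by 4 or more in about 43-44% of trials under simple randomisation, in 27% with a fixed 20/20 list, and in none of the simulated trials with stratified blocks.

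**5. Arm sizes under stratified blocks.** The final block in each stratum may be incomplete. Exactly 20:20 occurs in about 55-65% of trials (55-56% with blocks of 4 and 6), and 19:21 or better in 97.5-99.7%. The largest gap seen was 6 patients with blocks of 4 and 6, and 4 with the smaller blocks.

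**The case against.** A reader might infer from the wording that randomisation is unrestricted. The documents do not say so. A random number generator can produce a shuffled list of 20 and 20 or a blocked list, and the fixed arm sizes suit such a list at least as well as 40 independent draws. The 12.5% and 26.8% therefore apply only if the sequence is simple. The 5 foreseeable allocations need three further things: closing of the arm that fills first, which appears nowhere in the protocol; a simple sequence before that; and recruiters who keep count. Likewise, the text is silent on concealment, which does not show that allocation is unconcealed.

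It is also fair to say that chance imbalance under valid randomisation does not bias the treatment estimate. The 1-point yardstick is not tied to any mortality effect in the documents. Precision is limited by the total of 40 far more than by the split. Adjusting the analysis would deal with much of the MELD problem without stratifying, and an unstratified list is defensible in a single-centre pilot.

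Most of this stands, and it limits the claim. It does not remove the point about MELD, which holds under simple randomisation and under a fixed list alike, because the planned analysis makes no adjustment either. The pilot label does not settle the matter, since a between-arm comparison of mortality is the primary objective.

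**Conclusion.** The point holds as a cheap improvement, not as a flaw that invalidates the trial. Sequence type, restriction and concealment are unstated, and MELD is left uncontrolled at both the allocation and the analysis stage. On assumed SDs of about 2.2 to 2.9, the chance of a difference in mean MELD of 1 point or more is 16-28%, against about 1.5-4% with two-stratum blocking. The arm-size and predictability figures are conditional on readings that the text permits but does not state, and the loss of precision from uneven arms is small.

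Two stronger conclusions are not supported. One is that the mortality result will be confounded by MELD; the documents give no basis for sizing that effect. The other is that stratified blocks would guarantee 20:20 and equal MELD; they bring both close without ensuring either.

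**What to change.** Replace the randomisation sentence with a full description:

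- computer-generated permuted blocks of randomly varying size (for example 4 and 6), stratified by screening MELD (for example 12-16 v 17-21, the cut-point being the sponsor's choice);
- a list prepared and held by an existing department member who does not enrol patients;
- each allocation released only after eligibility and baseline data are recorded, for instance in sequentially numbered opaque sealed envelopes.

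Varying block sizes matter because small fixed blocks can be guessed in an open single-centre trial. State the target as about 20 per arm.

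In the Statistical Analysis section, adjust for baseline MELD. Use the baseline score as a covariate in the CTP, MELD and MELD-Na comparisons, and a MELD-stratified log-rank test for 180-day mortality. The section currently attaches the log-rank test to in-hospital survival, so the 180-day analysis needs naming.

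The cost is one list, a set of envelopes and a few sentences. No extra visit, test or patient is needed, since MELD is already required for entry. The drawback is that incomplete final blocks can leave the arms a few patients off 20:20.

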### **Pre FMT**

Participants randomized to the FMT arm will be given pretreatment antibiotics to decrease the host bacterial load, lower diversity, and enable a colonic colonization of the donor microbiota. Lactulose and rifaximin will be continued for all patients as per indication. A 5-day broad-spectrum coverage regimen will be used (metronidazole 500 mg orally three times daily, ciprofloxacin 500 mg orally twice-daily, and amoxicillin 500 mg orally three times daily) prior to administration of FMT. All antibiotics will be discontinued at least 12 hours before FMT to ensure that these agents would not impact the instilled microbiota. Participants in the SOC arm will not receive antibiotic pretreatment or FMT, but follow-up will be identical on days 7, 30 and 90 post FMT post randomization.

### **Donor Selection Criteria:**

Family members will be interviewed and screened for eligibility for being a FMT donor since pooled stool donor facility is not available at our institute. The subjects will be screened for routine laboratory tests, hemogram, fasting blood sugar, liver function tests, lipid profile, stool routine and microscopy for cysts, parasites, ova stool for occult blood, stool cultures, HBsAg, anti HCV, HIV 1 and 2, Clostridium difficile and VDRL. A written informed consent will be taken from the donor to donate fresh stool sample on day of FMT. Donors will be excluded if they had abnormal bowel motions, abdominal complaints, extensive travel history or predisposing factors for potentially transmittable diseases, occasional or chronic alcohol intake, and history of substance abuse or fail to provide consent. Subjects will also excluded if they are less than 18 or more than 60 years of age, had primary or secondary immunosuppressed state, had enteric infections within last 2 months, history of inflammatory bowel disease, prior abdominal surgery, pancreatic disease, gastrointestinal neoplasms in the past, metabolic syndrome, systemic autoimmunity, atopic diseases or on treatment for the same, food and respiratory allergies, chronic neurologic disorders, neuro-developmental disorders, have had antibiotics within the last 2 months. Donors will be advised to eat food based on recommended daily allowance as calculated by dietician and not permitted to eat street foods or attend public functions or eat at family functions or parties. They will not be allowed social consumption of alcohol or tobacco during a period of one week.

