## **Study population**

All patients with decompensated cirrhosis who will be admitted to the Department of Hepatology in Medical Ward Unit or Liver ICU of Postgraduate Institute of Medical Education and Research (PGIMER) or will be attending the outpatient department of PGIMER during the period from August 2018 till May 2019 will be screened for eligibility for enrollment after ethical approval from the institute ethics committee. An informed consent will be taken from all the participants. Those patients who satisfy the inclusion and exclusion criteria and provide a valid informed consent will be enrolled in the study.

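### FMT needs an eligible family donor, but randomisation does not, so a patient can be allocated to FMT with no donor and no stated rule for that case

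*Combined protocol and SAP*

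**What the plan says.** **Donor source.** The section Donor Selection Criteria states: "Family members will be interviewed and screened for eligibility for being a FMT donor". The reason given is that "pooled stool donor facility is not available at our institute". No back-up source is described. Stool is to be fresh: "A written informed consent will be taken from the donor to donate fresh stool sample on day of FMT". No frozen stock is described for the trial.

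**Donor eligibility.** A donor must be aged 18 to 60 and pass blood, stool and serology tests. The exclusions include "occasional or chronic alcohol intake, and history of substance abuse or fail to provide consent", and also earlier abdominal surgery, metabolic syndrome, atopy or allergy, and antibiotics in the past 2 months.

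**Patient eligibility and randomisation.** Under Study population: "Those patients who satisfy the inclusion and exclusion criteria and provide a valid informed consent will be enrolled in the study". There are three inclusion items (age, cirrhosis with MELD 12 to 21, capacity to consent) and seventeen exclusions. None refers to a donor. Under Randomization of patients, those "enrolled in the study after satisfying the selection criteria will be randomized into two groups 1:1 ratio using a random number generator".

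**Endpoint and analysis.** The primary objective is the difference in 180-day mortality between arms, with 20 patients per arm. The Statistical Analysis section names no analysis population. Follow-up post FMT counts days from the FMT procedure.

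**The concern.** The experimental treatment can be given only if a suitable relative exists, agrees, passes the tests and provides stool on the day. The route into the trial checks none of this. If donor screening follows randomisation, some patients may be allocated to a treatment that the site cannot deliver to them.

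There are two possible consequences, depending on how such patients are handled:

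- **Kept in the FMT arm.** The randomised comparison stays valid, but part of the arm has not received FMT. The observed difference in mortality is then smaller than the effect in patients who can be treated.
- **Removed from the FMT arm only.** That arm is then filtered on having a healthy, non-drinking, consenting relative, and the standard-of-care (SOC) arm is not. If family support is related to prognosis, the arms are no longer comparable.

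With 20 patients per arm, each affected patient is 5% of the FMT arm (1/20).

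**Working it through.** **Step 1: can it happen under the text as written?** Enrolment requires the listed criteria and consent. Randomisation requires enrolment. Neither requires a donor. FMT requires a family donor, and there is no pooled facility. A patient can therefore meet every written condition for allocation to FMT while having no eligible donor. The order of donor screening and randomisation is not stated, so the text allows this outcome but does not establish that it will occur.

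**Step 2: figures available.** The documents give 20 per arm, a 1:1 ratio, chi-square or Fisher's exact test, and P < 0.05. They give no effect size, mortality rates, power, dropout or donor failure rate, so the figure of 20 cannot be reproduced. Everything below is illustrative. The assumptions are a donor failure share f of 10%, 20% or 30%, 180-day mortality of 40% on SOC and 10% with FMT, and a two-sided test.

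**Step 3: dilution when analysed as randomised.** Assume that a patient without a donor has SOC mortality:

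- FMT-arm mortality = (1 − f) × 10% + f × 40%
- Difference = (1 − f) × 30 points
- Chance of at least one patient without a donor among 20 = 1 − (1 − f)^20
- Information, treating the variance as constant, ≈ (1 − f)²

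The variance of a proportion is not constant, so I also computed the n per arm for 80% power directly:

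n = [1.96·√(2p̄(1 − p̄)) + 0.842·√(p₁(1 − p₁) + p₂(1 − p₂))]² / (p₁ − p₂)²

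Here p₁ and p₂ are the two mortality rates and p̄ is their mean. For 40% versus 10% this is (1.200 + 0.483)²/0.09 = 31.5, so 32 per arm. Relative information is 32 divided by the n needed at each f.

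| f | Without donor, of 20 | Chance of at least one | FMT-arm mortality | Difference | (1 − f)² | n per arm, 80% power | 32/n | Power at 20 per arm: normal / Fisher |
|---|---|---|---|---|---|---|---|---|
| 0 | 0 | – | 10% | 30 points | 100% | 32 | 100% | 59.7% / 49.2% |
| 10% | 2 | 88% | 13% | 27 points | 81% | 41 | 78% | 48.9% / 38.1% |
| 20% | 4 | 99% | 16% | 24 points | 64% | 54 | 59% | 39.0% / 28.8% |
| 30% | 6 | 99.9% | 19% | 21 points | 49% | 73 | 44% | 30.2% / 21.4% |

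The shrinkage factor (1 − f) does not depend on the mortality rates chosen. The last three columns do, or rest on an approximation.

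**Step 4: bias if such patients were removed from the FMT arm only.** Assume no true effect, f = 20%, and mortality of 50% without a potential donor and 30% with one. SOC then shows 0.8 × 30% + 0.2 × 50% = 34%. The filtered FMT arm shows 30%. The apparent benefit is 4 points and is entirely spurious. By the same arithmetic it is 2 points at f = 10% and 6 points at f = 30%.

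**The case against.** **The site may screen donors first.** This is possible, and the documents do not rule it out. A reader might infer that patients are knowingly randomised before a donor is identified, but no section gives the order. Only the weaker statement stands: the written conditions permit it. The seventeenth exclusion, which leaves conditions hindering completion to the investigator's judgement, could be used to screen out a patient without a donor. It does not mention donors, so consistent use cannot be assumed.

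**Dropping and replacing is conjecture.** A reader might also infer that patients without a donor will be dropped and replaced to reach 20. No section mentions replacement, withdrawal or crossover for this reason, and Sample Size speaks only of consecutive eligible patients. The bias in Step 4 is therefore conditional. An as-randomised analysis would remove it, but not the dilution.

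**The failure rate could be close to zero.** Screening is not limited to one relative, so several could be tried. This stands, and it is why the figures are illustrations. Even with every donor available, 20 per arm gives power of only about 50% to 60% for an assumed 30-point difference, so donor failure is not the trial's main limit on power.

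**It is a pilot with a feasibility aim.** The Introduction says that the trial will assess feasibility and safety, and the share of patients with a usable donor is itself a feasibility result. Measuring the effect of offering FMT, donor failures included, is a legitimate choice. This objection has force: a donor requirement without a screening log would lose that result. But the primary objective is a between-arm mortality difference, and the plan does not say which effect it targets.

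**Conclusion.** The gap is real and of moderate weight. The plan makes FMT depend on a relative passing a long list of criteria, sets no donor condition for randomisation, and does not say when donors are screened or how a patient without one is handled or analysed.

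The certain part is structural: allocation to FMT without an eligible donor is possible under the text. The size is unknown. If a share f of the FMT arm has no donor and all patients are analysed as randomised, the expected difference is (1 − f) of what it would otherwise be. The associated loss of information rests on assumed failure rates and, for the direct sample-size figures, on an assumed 40% versus 10% mortality. It also assumes that a patient without a donor has SOC risk, which may not be exact if the donor fails after the 5-day antibiotic pretreatment has begun. Bias arises only if such patients are removed from one arm and donor availability is related to prognosis. The documents establish neither.

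They therefore do not support saying that the trial will be biased, or that it loses a known amount of power.

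**What to change.** 1. Add to the inclusion criteria that, before randomisation and for every patient whichever arm follows, at least one family member has agreed to donate and has passed the interview part of the existing donor criteria (age, history, alcohol, recent antibiotics). Laboratory and stool tests can stay with donors for patients allocated to FMT.
2. Keep a screening log of patients who are otherwise eligible but have no potential donor, so that the feasibility information is not lost.
3. State in Statistical Analysis that all randomised patients are analysed in their allocated arm, including those whose donor later fails laboratory or stool tests or cannot supply stool. Such patients have no FMT date, so their 180 days must be counted from a date that every randomised patient has, such as randomisation.

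**Cost.** A short interview with relatives of patients who turn out to be in the SOC arm, with no added laboratory tests. The results would apply only to patients with a potential family donor, although with no other donor source described these are the only patients whom the site could treat under this plan. Some late donor failures will remain, so the dilution is reduced but not eliminated.
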